RESEARCH PROTOCOL

Reducing Diagnostic Error to Improve Patient Safety in COPD and Asthma (REDEFINE Study)

Version: 1.5

Date: 1/11/2018

Principal Investigator: [name] MD MPH

Division of Pulmonary, Critical Care, Sleep, and Allergy, Department of Medicine, University of Illinois at Chicago, Chicago, IL

Sponsor: AHRQ 1R01HS024964-01

SPECIFIC AIMS AND HYPOTHESIS

Aim 1: Determine the prevalence of and characteristics associated with diagnostic error (DE) in asthma and/or COPD in an underserved population

Aim 2: Evaluate the effectiveness of the REDEFINE program compared to usual care on health care utilization and patient-centered outcomes (including respiratory medication use, all-cause emergency room visits, and all-cause hospitalizations)

Hypothesis:

The REDEFINE program will reduce health care utilization and improve patient-centered outcomes compared to usual care.

Aim 3: Evaluate the cost impact and cost effectiveness of the REDEFINE program versus usual care

Hypothesis:

The REDEFINE program will be cost-effective in the management of patients with COPD and asthma compared to usual care.

BACKGROUND AND SIGNIFICANCE

Asthma and chronic obstructive pulmonary disease (COPD) are common chronic lung diseases that are diagnosed in more than 30 million adults in the United States.^{1,2} However, diagnostic error (DE), considered one of the most common and harmful of patient-safety problems by the Institute of Medicine,^{3,4} occur frequently with asthma and/or COPD and disproportionately affect minorities and the underserved. DE leads to lost opportunities to identify other chronic conditions, avoidable morbidity and mortality, unnecessary costs to patients and health systems, and poor quality of care.³⁻⁶ Shortness of breath or dyspnea, which is a common symptom in asthma and COPD, is also common for many other chronic conditions such as cardiovascular disease and obesity. A better understanding of the impact of DE and interventions to improve diagnostic accuracy in asthma and COPD are of particular importance for minorities and the underserved that are disproportionately affected by conditions leading to dyspnea.

Spirometry is a simple, mobile, and essential test that is recommended by all major national and international guidelines for the diagnosis of asthma and COPD.⁷⁻¹⁰

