1. RESEARCH DESIGN

This will be a cluster-randomized comparative effectiveness trial conducted of patients with a primary care provider (PCP) diagnosis of COPD and/or asthma seen in outpatient primary care provider clinics (i.e. Family Medicine, Miles Square Health Center, and Academic Internal Medicine) as well as the CRC (Clinical Research Center) at the University of Illinois Hospital and General Internal Medicine and Family Medicine Clinics

at Cook County Health and Hospitals Systems (CCHHS). Providers will be randomized and their patients who fulfill the inclusion criteria will receive the intervention or be in the usual care group. Adults with a clinician-diagnosed COPD and/or asthma at high risk for diagnostic error due to lack of spirometry will undergo the REDEFINE intervention or usual care based on the PCP randomization. Outcomes will be assessed every 3 months for up to one year.

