2. ELIGIBILITY CRITERIA

A. Primary care provider (PCP) eligibility criteria:

Primary care providers (PCPs) will include physicians and nurse practitioners. PCPs specializing in internal medicine or family medicine with at least one half day per week outpatient clinic session at the following clinics will be eligible for the study:

- UI Health: Family Medicine (FM) clinics, Academic Internal Medicine (AIM) clinics
- Miles Square Health Center (MSHC)
- Clinical Research Center (CRC) at UIC
- Cook County Health and Hospitals Systems (CCHHS): General Internal Medicine (GIM) and Family Medicine

B. Patient eligibility criteria:

Inclusion criteria:

1. Age ≥ 40 years of age
2. Use of a maintenance respiratory medication and one of the following in the past year:
 - a. diagnosis of asthma
 - b. diagnosis of COPD, emphysema, or chronic bronchitis
3. No spirometry test performed in the past 3 years
4. Past or current smoker

Exclusion criteria:

- Unable to perform adequate spirometry
- Non-English speaking
- Pregnancy
- Plans to move from the Chicago area within the next year
- Seen by pulmonary or allergy specialist in the past 3 years
- Any terminal illness with a life expectancy of < 6 months
- Life threatening (e.g. Intensive care admission and/or use of mechanical ventilation) respiratory failure event in the past year

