4. DESCRIPTION OF PROCEDURES

A) PCP Education and Randomization:

After obtaining PCP informed consent and prior to patient recruitment, a one hour educational session will be held for PCPs participating in the study. The purpose of this session is to provide education to PCPs about COPD, asthma, spirometry, and GOLD and GINA guidelines (GOLD=Global Initiative for Chronic Obstructive Lung Disease, GINA=Global Initiative for Asthma). The educational session will provide continuing medical education credit to those who attend. The learning objectives will be the following: 1) Review COPD and asthma disease definition, presentation, diagnosis and testing including spirometry, 2) be familiar with the GOLD and GINA guidelines and recommendations for therapy.

PCPs who consented to participate in the study and completed the education session will be randomized to have their patients who meet the study criteria receive the intervention or usual care.

B) Patient subject- Intervention:

On the day of the outpatient visit, subjects will be advised to arrive 90 minutes prior to their clinic visit in the same building as the clinic site or the CRC (Clinical Research Center at UIC). The following information will be collected and procedures will be performed:

1. Subject demographic and contact information
2. Co-morbid conditions
3. Smoking history
4. Medication history from patient and also from pharmacy used by subjects
5. A respiratory exacerbation history in the past year
6. Modified Medical Research Counsel (mMRC) dyspnea scale and COPD Assessment Test
7. Quality of life measures
8. Pre and post-bronchodilator (BD) spirometry
9. De-Escalation Spirometry Screener for patients de-escalating based on spirometry (See Based on spirometry findings)
10. De-Escalation Phone Script

Based on spirometry findings:

1. If the spirometry findings are consistent with COPD and/or asthma, the following will be provided to the provider and patient to have available during the clinic visit: a letter summarizing the interpretation of the findings using GOLD/GINA criteria with recommendations for initial guideline driven therapy based on GOLD/GINA guidelines. Subjects will be managed by their PCP thereafter.

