2. If the spirometry findings are normal, with approval from the PCP, will de-escalate respiratory medication therapy via a stepwise process and schedule patient back for a repeat pre and post bronchodilator spirometry within 1-2 weeks at the same time and place as the PCP clinic session or the CRC (Clinical Research Center at UIC). Again with the PCP approval, this

deescalation and repeat spirometry can occur in 1-2 week intervals until all maintenance medications are discontinued as long as the pre and post spirometry continues to be normal. After each visit, the following will be provided to the provider and patient: a letter summarizing the interpretation of the findings using GOLD/GINA criteria with recommendations for initial guideline driven therapy based on GOLD/GINA guidelines, if appropriate. Subjects will be managed by their PCP thereafter.

3. All spirometry test results and the subject's assessment at the time of the test will be uploaded into the subject's electronic health record for future reference.

C) Patient subject- Usual Care:

On the day of the outpatient visit, subjects will be advised to arrive 60 minutes prior to their clinic visit in the same building as the clinic site or the CRC (Clinical Research Center). The following will be performed.

1. Subject demographic and contact information
2. Co-morbid conditions
3. Smoking history
4. Medication history from patient and also from pharmacy used by subjects
5. A respiratory exacerbation history in the past year
6. Modified Medical Research Counsel (mMRC) dyspnea scale and COPD assessment test
7. Quality of life measures

Subjects will be advised to go to their clinics and be managed by their PCP thereafter.

At the end of the 1 year followup, the patient will be scheduled for a pre and post BD spirometry and undergo the same spirometry protocol (de-escalation protocol) as the intervention group.

Based on spirometry findings:

1. If the spirometry findings are consistent with COPD and/or asthma, the following will be provided to the provider and patient: a letter summarizing the interpretation of the findings using GOLD/GINA criteria with recommendations for initial guideline driven therapy based on GOLD/GINA guidelines. Subjects will be managed by their PCP thereafter.

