Intervention: Subjects will receive \$95 in cash at the time of their last visit in-person.

Usual Care Group: Subjects will receive \$95 in cash at the completion of the 1 year spirometry and follow-up.

Additional spirometry visits after de-escalation of therapy:

Same for Intervention and usual care groups (except the intervention group will receive this near the beginning of the study and usual care group will receive this near the end of the study): Subjects will be provided a \$50 in cash for each additional spirometry visit.

2.A. Provision to compensation: If human subject receives over \$200.00 within one (1) calendar year, it is incumbent for the study staff to obtain the subject's social security number based on the OBFS guidelines. However, if human subject receives a total under \$200.00 within the calendar there is no need to obtain social security number from the human subject.

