5. STATISTICAL ANALYSES

All data will be stored in a secure, locked location. Data will be entered and managed through the Research Electronic Data Capture (REDCap). REDCap is a secure web-based application for building and managing online databases. REDCap is provided by

the CCTS Design Analysis Core. Data will be analyzed for clinical effectiveness using intention-to-treat principles.⁶⁹⁻⁷¹ For **Aim 1**, we will evaluate the misdiagnosis rates of the intervened and usual care groups separately at the first visit. Then compare rates between groups by using a generalized linear mixed model for binary outcome with two cluster levels, PCP and hospital, to account for the dependence within clusters. For the **Aim 2**, to investigate the impact of the misdiagnosis over time (4 time points: 0, 3, 6, 9, 12 months) on the quality of life and healthcare utilization, we will fit generalized linear mixed models with time, group, and their interaction as the main predictors. Two cluster levels, PCP and hospital, will be specified in the model to account for the dependence within clusters^{72,73} and an appropriate link function will be used for each outcome. Clinical important confounders will also be adjusted in the models. Before these analyses we will use descriptive statistics to describe the sample, and any assumption behind each statistical method will be examined during the analysis. A two-sided p-value less than 0.05 would be considered as statistical significance. All the analyses will be conducted by using SAS 9.2 (SAS Inst., Cary, NC).

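### Aim 1 compares misdiagnosis rates between arms at the first visit, but usual care has no study spirometry until the end of the 1-year follow-up

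*Combined protocol and SAP*

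**What the plan says.** Section 5 (Statistical Analyses) gives one analysis plan for Aim 1: "we will evaluate the misdiagnosis rates of the intervened and usual care groups separately at the first visit". A generalized linear mixed model for a binary outcome, with PCP and hospital as cluster levels, then compares the groups.

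Section 4 (Description of Procedures) sets the tests. Item 8 of the intervention arm's first-visit list (4.B) is "Pre and post-bronchodilator (BD) spirometry". The usual-care list (4.C) has seven items and no spirometry. For that arm the protocol states: "At the end of the 1 year followup, the patient will be scheduled for a pre and post BD spirometry". The compensation text (4.F) agrees, since the usual-care final payment is made "in cash at the completion of the 1 year spirometry and follow-up".

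Eligibility (section 2.B) requires "No spirometry test performed in the past 3 years" and excludes patients who are "Unable to perform adequate spirometry". Section 1 describes the population as "at high risk for diagnostic error due to lack of spirometry". The first primary outcome in 4.D is correct classification as COPD and/or asthma, with no definition or time point.

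**The concern.** A first-visit misdiagnosis rate needs a reference test at the first visit, and one arm has none. The analyst would have to improvise, and the obvious step is to use the month-12 usual-care tests. That sets month 0 in one arm against month 12 in retained patients of the other, and a difference could be taken for an effect of the program.

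At stake are the usual-care rate and the between-arm comparison in Aim 1. Primary outcome (i) is affected too: no other analysis in section 5 covers it, because the Aim 2 models name quality of life and health care utilization.

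**Working it through.** The documents give no figure to reproduce here. The main check sets the schedule beside the analysis; the arithmetic then sizes the workaround and the remedy.

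**1. What is available at the first visit**

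| Source | Intervention | Usual care |
|---|---|---|
| First-visit list (4.B, 4.C) | Spirometry, item 8 | Seven items, no spirometry |
| Arrival before clinic | 90 minutes | 60 minutes |
| Additional V0 list (4.E.1) | No spirometry added | No spirometry added |
| First study spirometry | First visit | End of 1-year follow-up |

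Usual-care patients scheduled for first-visit study spirometry: 0. The shorter arrival time suggests that this is deliberate. Eligibility rules out a clinical test in the past 3 years; an older one may exist, but no listed V0 item collects it. Other pulmonary function tests are recorded at the 3-monthly contacts, which come after V0. With the outcome present in one arm only, the group effect cannot be estimated.

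**2. Reading the first visit as each arm's first spirometry visit**

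The model can then be fitted, but arm coincides with time, a year of management and retention. Inability to perform spirometry could also come to light through a study test at month 0 in one arm and only at month 12 in the other.

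Let p be the true rate in both arms, and let a and b be the proportions of misdiagnosed and correctly diagnosed patients retained to month 12. The observed usual-care rate is pa / [pa + (1−p)b]. The 30-50% range for p is from the Background; a and b are assumptions.

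- p = 0.30, 85%/75%: 0.255/(0.255 + 0.525) = 0.327; reversed 0.274.
- p = 0.40, 85%/75%: 0.340/(0.340 + 0.450) = 0.430; reversed 0.370.
- p = 0.50, 85%/75%: 0.425/(0.425 + 0.375) = 0.531; reversed 0.469.
- p = 0.40, 90%/70%: 0.360/(0.360 + 0.420) = 0.462; reversed 0.341.

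To see how often this bias alone gives p < 0.05, take a Wald test of 0.40 (n = 250) against the biased rate (n = 195 to 205 retained). Each variance is multiplied by 1 + (m−1)×ICC, where m is patients per PCP, the ICC is 0 to 0.05 and there are 40 to 80 PCPs. The rejection rate is 0.082 to 0.099 for the 85/75 split and 0.182 to 0.256 for 90/70, against a nominal 0.05.

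**3. If both arms had first-visit spirometry**

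The quantity would precede any program effect, so the comparison would show baseline balance or recruitment selection. It would also leave out the second half of Aim 1, the characteristics associated with error.

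**4. What the intervention arm alone can deliver**

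The protocol plans about 500 patients and at most 80 PCPs. It gives no allocation ratio; 1:1 is assumed, so n = 250. Half-width = 1.96 × √[p(1−p)/250 × DE], with DE = 1 + (m−1)×ICC and m = 500/PCPs.

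- p = 0.40, ICC 0.05, 80 PCPs: m = 6.25, DE = 1.2625, half-width 0.068.
- p = 0.40, ICC 0.05, 40 PCPs: m = 12.5, DE = 1.575, half-width 0.076.
- Smallest in the range examined (p = 0.30, ICC 0.01, 80 PCPs): 0.058.
- Largest (p = 0.50, ICC 0.10, 40 PCPs): 0.091.

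Errors available for the characteristics model: 250 × 0.30 = 75 to 250 × 0.50 = 125.

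**The case against.** The strongest reply is that the first visit may refer to the diagnosis held at entry, with the month-12 test serving usual care as a delayed reference standard. The arm does eventually follow the same spirometry protocol, so its data would be late and incomplete, not absent. The text does not say this, and the reading meets the problems in step 2 of the working: verification a year later, in retained patients only.

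Other objections stand in part:

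- The intervention-arm rate can be estimated as written. What fails is the usual-care rate and the comparison, and no stated hypothesis depends on them, since hypotheses are given only for Aims 2 and 3.
- The link between the Aim 1 rate and primary outcome (i) is inferred. Without the link, though, that outcome has no assigned analysis at all.
- Patients are recruited after PCPs are randomized, so a true baseline comparison could reveal recruitment selection. That has some use, but it needs first-visit tests in both arms.
- The retention splits are not from the documents, and they measure a workaround the plan does not propose. The 85/75 result is modest. The intervals ignore clustering by hospital and assume equal clusters.

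None of this supplies a first-visit outcome for usual care.

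**Conclusion.** The concern holds, and the plan must be corrected before analysis. The Aim 1 comparison has a first-visit outcome in one arm only. This rests on judging misdiagnosis by spirometry, which the documents support without defining it; no alternative that could be scored at V0 is given. Other V0 data, such as history, medications and questionnaires, are collected in both arms.

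The conclusion comes from the schedule and does not depend on the illustrative figures. Those indicate a bias in the usual-care rate of about 3 points under the 85/75 split and about 6 points under 90/70 at a true rate of 40%. Primary outcome (i) has no usable analysis as the plan stands.

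**What to change.** 1. Delete the between-arm first-visit test.
2. Estimate the prevalence of diagnostic error from the intervention arm's first-visit spirometry, with a confidence interval that allows for clustering by PCP. Write a definition covering both kinds of error in the Background: neither disease present, and asthma confused with COPD. Add a sensitivity analysis using status at the end of any repeat-spirometry sequence, noting that the sequence depends on PCP approval.
3. Report the usual-care month-12 rate separately as an estimate in retained patients, and give the numbers excluded for inadequate spirometry by arm.
4. Fit a mixed logistic model for diagnostic error on baseline characteristics.
5. State the definition, time point, reference test and analysis for primary outcome (i), and reconcile them with the spirometry schedule. If arms are compared on whether the month-12 chart diagnosis agrees with spirometry (in usual care, before its letter is issued), state three limits: the reference test is dated differently by arm; usual care is restricted to retained patients; and agreement in the intervention arm is partly built in, because results go to the PCP and the chart. It should not be presented as an unconfounded program effect.

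Items 1 to 4 cost only SAP wording. Item 5 adds one chart-diagnosis field at the existing month-12 review if that comparison is kept. The price is that baseline prevalence rests on about half the patients, and no unconfounded between-arm claim on primary outcome (i) is possible under the current spirometry schedule.

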2. If the spirometry findings are normal, with approval from the PCP, will de-escalate respiratory medication therapy via a stepwise process and schedule patient back for a repeat pre and post bronchodilator spirometry within 1-2 weeks at the same time and place as the PCP clinic session. Again with the PCP approval, this deescalation and repeat spirometry can occur in 1-2 week intervals until all maintenance medications are discontinued as long as the pre and post spirometry continues to be normal. After each visit, the following will be provided to the provider and patient: a letter summarizing the interpretation of the findings using GOLD/GINA criteria with recommendations for initial guideline driven therapy based on GOLD/GINA guidelines, if appropriate. Subjects will be managed by their PCP thereafter.
3. All spirometry test results and the subject's assessment at the time of the test will be uploaded into the subject's electronic health record for future reference.

D) Outcome Measures:

1. Primary outcome:

- (i) Accurate classification of patient as having COPD and/or asthma
- (ii) All-cause and respiratory related, acute care outpatient visits, ED visits, and hospitalizations

2. Secondary outcome:

- (i) Appropriate use of respiratory medications based on guidelines
- (ii) Use of other diagnostic testing: ECG, echocardiograms, CT/CXR, stress testing, cardiac catheterization, other pulmonary function tests
- (iii) Initiation of guideline based therapy
- (iv) Quality of life measures

E) Data collection and follow-up

1) Baseline data collection obtained at visit zero (V_0), in addition to those listed under intervention and usual care:

- 1. Demographic data (gender, age, self-reported race)
- 2. SES related measures: median household income
- 3. Level of education
- 4. Type of health insurance or self-pay
- 5. Up to two emergency contacts information
- 6. List of current respiratory medications from subject's pharmacy and verification with patient
- 7. Co-morbidities
- 8. History of prior ED visits or hospitalizations in the past one year with associated cause
- 9. EQ-5D 5L +B Bolt-on
- 10. SF-36 short form
- 11. Social support survey

2) All subjects will have their medical charts reviewed every 3 months after the initial visit (MR_1 , MR_2 , MR_3 , MR_4) up to one year. These electronic medical chart reviews will be used to obtain follow-up data since last study contact.

- 1. Change in type of health insurance or self-pay

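### Aim 1 takes the misdiagnosis rate at the first visit, before the intervention arm's planned repeat spirometry and about a year before usual care has any spirometry

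*Combined protocol and SAP*

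**What the plan says.** Section 5 (Statistical Analyses) fixes the Aim 1 time point for both arms: "we will evaluate the misdiagnosis rates of the intervened and usual care groups separately at the first visit". The rates are then compared between groups with a mixed model for a binary outcome.

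Section 2.B requires "Use of a maintenance respiratory medication and one of the following in the past year", the listed alternatives being a diagnosis of asthma or one of COPD, emphysema or chronic bronchitis.

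Section 4.B lists "Pre and post-bronchodilator (BD) spirometry" among the intervention arm's first-visit procedures. What follows a normal result is also set out there: "If the spirometry findings are normal, with approval from the PCP, will de-escalate respiratory medication therapy via a stepwise process", with repeats at intervals of one to two weeks "until all maintenance medications are discontinued as long as the pre and post spirometry continues to be normal".

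Section 4.C gives usual care the same baseline history and questionnaires but no spirometry at that visit. Instead, "At the end of the 1 year followup, the patient will be scheduled for a pre and post BD spirometry", followed by the same de-escalation procedure.

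Section 4.D names primary outcome (i) as "Accurate classification of patient as having COPD and/or asthma". It gives no test, time point or medication state. No other section defines misdiagnosis or diagnostic error by test result.

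**The concern.** A normal result in someone taking maintenance treatment has two explanations: there is no airway disease, or there is disease that treatment is controlling. Section 4 does not let one normal test end the evaluation; with the PCP's approval it steps medication down and tests again. Section 5 brings none of those later tests into the rate. If the first test decides, a patient who is normal at first and obstructed on a later test would be recorded as a diagnostic error although the study has just found the disease.

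The usual-care side is more direct. The sentence in section 5 covers both groups, but one of them has no spirometry at the visit it names.

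Prevalence of diagnostic error is the whole of Aim 1, and accurate classification is a primary outcome. The analysis of characteristics associated with error would be affected too, because well-controlled patients could enter it as misdiagnosed.

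**Working it through.** The plan gives no expected Aim 1 rate, power, intracluster correlation (ICC) or effect size, so there is no figure to reproduce. The check is of timing first, then illustrative arithmetic.

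**Timing by arm**

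| | Intervention (4.B) | Usual care (4.C) |
|---|---|---|
| First visit | Pre/post spirometry | No spirometry |
| After a normal test | De-escalation and repeats every 1-2 weeks, if the PCP approves | Same, but only after the one-year test |
| Time point of the rate (section 5) | First visit | First visit |

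The stated time point precedes the repeat tests in one arm and every test in the other.

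**Direction.** Repeat testing follows only a normal result. Later tests can therefore take patients out of the normal-spirometry error group but cannot add any. A patient who reverses but shows the other disease (asthma instead of COPD, or the reverse) remains an error of a different type. The sums below assume that every reversal confirms the recorded label. Where that fails, the overstatement of the total error rate is smaller.

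**Size.** Inputs:
- p, share of first tests that are normal: 30-50%, assumed. It borrows the literature misdiagnosis range in Background and Significance, which is not itself a rate of normal first tests.
- f, share of those that reverse as medication is withdrawn: 10-30%, assumed.

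Overstatement = p × f.
- Low: 0.30 × 0.10 = 0.03, or 3 points.
- High: 0.50 × 0.30 = 0.15, or 15 points.

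The points do not depend on arm size. In patients, assuming 250 per arm, this is 250 × 0.03 = 7.5 to 250 × 0.15 = 37.5. The 250 in section 3 is per health system; the split by arm is not stated.

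**Against sampling error.** The 95% half-width for one arm of 250, ignoring clustering, is 1.96 × √(p(1−p)/250): 5.7 points at p = 0.30 and 6.2 at p = 0.50. The low end of the illustration is within sampling error and the high end is well beyond it. At f = 20% the overstatement is 6 to 10 points.

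**If the arms were classified at different stages.** Suppose intervention patients were classified on the first test and usual-care patients at the end of their sequence, with no real difference between arms. The rates compared are p and p(1−f). With n per arm and p̄ the mean of the two rates p₁ and p₂, the chance of p < 0.05 is about Φ(z), where

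z = [(p₁−p₂) − 1.96√(2p̄(1−p̄)/n)] / √[(p₁(1−p₁)+p₂(1−p₂))/n].

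For p = 0.40, f = 0.20, n = 250: z = (0.08 − 1.96 × 0.0429)/0.0428 ≈ −0.10, so Φ(z) ≈ 0.46. For clustering, 500 patients over at most 80 PCPs is 6.25 each. An assumed ICC of 0.05 gives a design effect of 1 + 5.25 × 0.05 = 1.26 and an effective n of about 198.

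| Normal first tests, p | f = 10% | f = 20% | f = 30% |
|---|---|---|---|
| 30% | 0.11 / 0.10 | 0.33 / 0.27 | 0.64 / 0.54 |
| 40% | 0.15 / 0.13 | 0.46 / 0.38 | 0.81 / 0.71 |
| 50% | 0.20 / 0.17 | 0.61 / 0.52 | 0.93 / 0.86 |

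(ICC 0 / ICC 0.05.) If both arms were classified on a first test, much of the error would be shared and these figures would not apply.

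**The case against.** The strongest reply is that the plan nowhere says a normal first test makes a patient misdiagnosed. A reader might infer that controlled disease is in fact counted as error, but with no case definition that goes too far. The time point could instead mean the diagnosis the patient carried at baseline, judged on whatever tests follow. The lack of first-visit spirometry in usual care even favours that reading, since a first-visit test result cannot be what is meant in both groups. This stands, and it makes the bias conditional. It does not rescue the text, because section 5 does not give the alternative reading and an analyst following it literally would use a single early test in one arm and nothing in the other.

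A reader might also infer that every patient is on treatment when first tested. Section 2.B requires use within the past year, not on the test day, so use is likely but not guaranteed. Nor does section 4 say that de-escalation settles the classification: it describes something that can happen with the PCP's approval.

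Finally, the reversal share is unsupported by the documents, and the low end of the illustration is smaller than the sampling error. Both objections to size are fair.

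**Conclusion.** The point holds in conditional form. As written, the Aim 1 rate is tied to a time point before the intervention arm's repeat tests and before any usual-care spirometry. If the first test decides, errors of the normal-spirometry type are overstated, and the between-group comparison cannot be made from spirometry at that visit.

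The 3-15 point range is an illustration resting on assumed values of p and f and on reversals confirming the recorded label; it is not an estimate. The false-difference probabilities also assume 250 per arm and classification at different stages, which the plan does not state.

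Confidence is high that sections 4 and 5 must be reconciled, moderate on direction and low on size.

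**What to change.** In section 5, replace the first-visit time point with classification of the baseline diagnosis from all tests in each arm's planned spirometry sequence, and apply the same definition to primary outcome (i) in section 4.D. Use these classes:

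1. Confirmed, label matches.
2. Confirmed, label differs (asthma versus COPD, which Background and Significance treats as diagnostic error).
3. Not confirmed: spirometry normal after maintenance medication has stopped.
4. Abnormal, but not consistent with COPD or asthma; state in advance how this is counted.
5. Unresolved: a normal test, with de-escalation not approved or not completed.

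Report prevalence with two bounds, counting all unresolved patients first as error and then as no error. Report separately any usual-care patients who never have the one-year test. Keep the first-test rate as a sensitivity figure, labelled on-treatment and shown with recorded medication status. State that the usual-care sequence is measured about a year later, so that even under a common definition the between-arm comparison of rates is limited.

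The cost is analysis wording. The repeat tests are already planned and their results uploaded to the health record, and no patient's management changes. The downside is that prevalence may fall and will carry bounds. If 20% of normal first tests were unresolved (assumed), the bounds would be 0.30 × 0.20 = 6 to 0.50 × 0.20 = 10 points apart.
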